### AIM 3: Prospectively assess the accuracy of our HRCA system in predicting clinically significant dysphagia and aspiration in a randomized, controlled trial.

**A3.a. Introduction:** For Aspirometer-based swallowing screening to be useful in clinical settings, it needs to outperform SIS in identifying patients at risk of silent aspiration and clinically significant dysphagia before they are placed at risk of aspiration pneumonia, or its further development is not warranted. The objective of this aim is to establish the superiority of dysphagia screening with the Aspirometer to the existing non-instrumental SIS protocols. To attain the objective of this aim, we will test the working hypothesis that the Aspirometer combined with, and independent of, SIS will identify VF-confirmed clinically significant OPD more accurately than SIS alone. We will use an approach that screens consenting patients with ordinary SIS and HRCA, and compare four levels of screening predictions (SIS human judgment criterion only, HRCA criterion only, SIS and HRCA criteria, SIS or HRCA criteria) for identifying dysphagia as measured from gold standard VF testing of all participants performed within 24 hours of screening. The rationale for this aim is that a clinically useful and accurate HRCA-based instrumental screening method not only needs to be rigorously tested against current practices to establish its validity and accuracy, but also needs to be examined for possible incorporation into current clinical practices. The acquisition of such knowledge is critical to the improved mitigation of unnecessary and adverse health sequelae associated with OPD. Based on our preliminary data, we expect that HRCA-based screening will be able to identify (sensitivity=) 90% or more of patients with OPD needing intervention or follow-up with gold standard VF testing and (specificity=) 90% of those not needing VF testing using one of the 3 strategies incorporating HRCA. This would validate the development of HRCA-based swallow screening tools that pre-emptively identify patients with a high pneumonia risk due to OPD, expedite intervention or gold standard swallowing diagnostic tests when necessary, and to reject the need for VF testing when unnecessary.

**A3.b. Justification and feasibility – Review of relevant literature:** SIS should rely on well-tested protocols that can detect true occurrences of OPD during screening, in comparison to subsequent gold-standard instrumental assessments [22, 130, 131, 132]. Though several SIS have been proposed and standardized in the literature (Table 3), previous SIS research contained confusing evidence [16, 21] by using different thresholds to define the presence of OPD. The most commonly reported screening metrics are sensitivity (the percentage of patients with an underlying problem, who are correctly

**Table 3 – Sensitivity and specificity of screening protocols for aspiration.**  
SENS = Sensitivity; SPEC = Specificity; FPR = False Positive Rate; FNR = False Negative Rate.

Test	SENS	SPEC	FPR	FNR
Volume-Viscosity Screening Test	100%	29%	72%	0%
Daniels Swallow Screen	92%	66%	33%	8%
Gugging Swallow Screen	100%	50%	50%	0%
Yale Swallow Protocol	100%	44-64%	36-56%	0%

classified) and specificity (the percentage of patients without an underlying problem, who are correctly classified). When compared to blinded ratings of nonconcurrent instrumental exams, swallow screenings err on the side of over-identifying aspiration risk, i.e., good sensitivity but poor specificity (see Table 3). While it may be argued that this bias in favor of sensitivity constitutes a conservative “safety net” for finding swallowing difficulties, it also results in unnecessary interventions for patients without significant OPD (Figure 3) including withholding oral dietary intake and diet texture restrictions, placement of feeding tubes, and unnecessary referrals for costly assessments, all of which affect quality of life and place financial and other burdens. A screening protocol should be performed in ordinary settings by typical screening staff, and detect OPD accurately while incurring minimum risk for the patient. Our approach to this aim will produce results that can demonstrate superior identification of both people with and without OPD compared to prior OPD screening research which exhibits zero identification of silent aspiration and only about 60% identification of those without OPD.

### **A3.c. Justification and feasibility – Preliminary studies:**

In our initial study [31], we collected time-linked HRCA signals and VF, using a protocol of three sips of thin liquid barium (5 cc each). The classification algorithms were trained to discriminate swallows with PAS scores of 1 and 2 (safe) from those with scores  $\geq 3$  (penetration of material into the airway, above the level of the vocal cords, without clearance) and succeeded in this task at the level of the single bolus with 90% sensitivity and 77% specificity.

[figure not shown]
When all the swallowing tasks performed by each patient were considered in aggregate, sensitivity for the detection of aspiration (i.e., anywhere in the protocol) improved to 100%, but specificity fell to 54%. These details are summarized in Table 4. Next, [name] has used HRCA signals collected from 30 older adults [101] to develop a support vector machine classifier to distinguish between grossly safe and unsafe swallowing with high sensitivity ( $97.1 \pm 2\%$ ) and modest specificity ( $64 \pm 8.8\%$ ). Also, we used HRCA signals from 29 pediatric participants along with a support vector machine classifier to achieve an adjusted accuracy of  $89.6\% \pm 0.9$  for the discrimination between swallows with and without airway entry [102]. Most recently, [name] has used a Bayes’ machine learning approach to infer about the airway protection in 40 patients with dysphagia [105]. This was the first study that demonstrated that we can grossly differentiate healthy swallows (P-A scores  $\leq 3$ ) from penetration-aspiration swallows (P-A scores 4-8) with an accuracy greater than 90%. These preliminary results demonstrate that we can reliably differentiate safe and unsafe swallowing events.

### **A3.d. Experimental approach:** The main goal of this aim is to demonstrate that the proposed HRCA tool is objective and can improve upon the accuracy of SIS alone in identifying participants who have OPD and need to undergo a VF exam or need immediate intervention (Figure 11). To achieve this goal, we will carry out the following experimental steps:

STEP 1: Enroll 50 consenting patients eligible for SIS in the experiment, and perform combined SIS screening and an HRCA screening. STEP 2: The HRCA system will be applied to all patients. The dysphagia SIS screen employed in the University of Pittsburgh Medical Center Presbyterian University Hospital will be performed, which consists of two or three 5mL water swallows and drinking 90mL of water at a self-selected pace. STEP 3: Nurses or other staff (non-SLPs or physicians) administering the screens and blinded to the HRCA output, will score the screens on the basis of the institutional SIS algorithm, denoting any signs of OPD or penetration/aspiration (e.g., wet voice, coughs) for each swallow that is observed. For the concurrent HRCA screening, we will record and denote the output of the algorithm for each observed swallow with findings from Aims 1 & 2. STEP 4: We will administer a VF exam for all patients using clinical protocols that include the same bolus conditions (5mL thin liquid, 30mL thin liquid) of swallowed material used in the SIS, within a 24-hour period to confirm the presence or absence of dysphagia/aspiration. STEP 5: The MBSImP, the PAS and the Normalized Residue Ratio Scale will be used to measure swallow impairment, airway protection and post-swallow pharyngeal residue. These measures will be made by our trained laboratory associates. STEP 6: HRCA, SIS, and VF results will be compared.

**Table 4 –** HRCA-based screening can detect aspiration, validated against concurrent VF. SENS = Sensitivity; SPEC = Specificity; FPR = False Positive Rate; FNR = False Negative Rate; PB = Per bolus; PP = Per participant.

Parameter	Statistic	PB	PP
Impaired Swallowing Safety (13/40 patients; 55/154 swallows)	SENS	90%	100%
	SPEC	77%	54%
	FPR	23%	48%
	FNR	10%	0%

**Figure 12 –** Our proposed experimental and data analysis approach for Aim 3.

**A3.e. Data interpretation:** We will fit a series of logistic regression models with presence/absence of clinically significant OPD/aspiration as the dichotomous dependent variable, and HRCA signatures and SIS, both individually and in combination, as the independent variables. We will use areas under ROC curves (c-statistics) as measures of predictive accuracy, and compare them using DeLong's method [133]. We anticipate that the c-statistics for the 3 models involving HRCA will be significantly greater than that using SIS alone.

**A3.f. Expected outcomes:** The benchmark for success of Aim 3 will be a successful completion of proposed testing of the HRCA-based screening in a clinical setting yielding accurate identifications of patients at risk of silent aspiration. Specifically, we will: (1) test the HRCA-based screening in clinical settings and denote its accuracy; (2) understand if confounding clinical factors can affect the deployment of the HRCA-based screening (not expected from our preliminary work). Successful completion of this aim will demonstrate that the Aspirometer (HRCA and advanced data analytics) can conveniently, noninvasively, and inexpensively produce robust predictions of OPD presence and absence that are measurably superior to SIS, and produce some diagnostic results currently possible only with VF testing.

**A3.g. Challenges and contingency plans:** The preliminary results (see A3.c.) strongly support our hypothesis (see A3.a.). In the highly unlikely event that our judges' PA or MBSImP score ratings drift unacceptably, we will increase surveillance on inter- and intra-rater reliability and pull judges from analysis and retrain them to criterion, retest their reliability before placing them back online.

**A3.h. Sample size justification:** We plan to recruit 50 patients, with an anticipated effective sample size of 46 after refusals. Assuming that approximately 50% of recruits will have clinically significant dysphagia/aspiration, a correlation of approximately 0.3 between SIS and HRCA, and an area under ROC curve of  $c=0.600$  for SIS alone, with the proposed sample size, we will have 80% power to detect an increase in area under ROC curve as small as 0.240 at  $\alpha=0.05$  with one of the 3 strategies that involve HRCA [134, 135].

**Project coordination and management:** [name] will direct the study and will lead the analysis and algorithm

testing components of the study. [name] will lead the analysis of the VF images and clinical aspects of the study and be responsible for clinical dissemination of our results. Drs. [name] and [name] have jointly or separately

AIMS AND ACTIONS	Year 1				Year 2				Year 3				Year 4				Year 5			
	Q1	Q2	Q3	Q4																
AIM 1. Collect and analyze data from healthy controls																				

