**Figure 9 – Preliminary results for Aim 1.** Using different configurations of artificial neural networks, we can achieve very high accuracies. In this case, a 1-layer combination of two large 2-layer networks for each axis provided the best results (bolded above).

greater sensitivity than our single-axis networks. But we do not have concurrent VF validation of the data obtained from the healthy people. Collection and analysis of these data will complete the range of swallow function and enable completion of our 2nd and 3rd aims, which seek to develop an HRCA impairment severity continuum.

**A1.d. Experimental approach:** STEP 1: We will collect concurrent VF and HRCA recordings from 70 healthy subjects (35 females and 35 males) with no previous history of swallowing difficulties who are age matched to our database of swallows from patients with OPD. Each subject will complete five swallows of 3mL thin liquid and five swallows of self-selected, comfortable volume of thin liquid from a cup, in a head-neutral position. STEP 2: We will first measure nine kinematic measures with VF (onset, offset, and time to peak hyolaryngeal excursion; laryngeal closure and reopening; UES closure and reopening; onset and offset of tongue base to posterior wall contact), penetration-aspiration scale scores [109], and pharyngeal retention/residue scores [89, 110, 111, 112].

STEP 3: Pre-process all HRCA recordings per steps taken in previous publications [29, 30, 71], to remove any disturbances and diminish noise in these recordings. STEP 4: VF results (STEP 2) will be equated with HRCA signal features and categorized by bolus volume of the swallowed material, these data will be combined with the data from over 4000 patient swallows from our previous R01 grant.

[figure not shown]

Figure 10 – Our proposed experimental and data analysis approach for Aim 1.

STEP 5: We will develop an algorithm based on the state-of-the-art machine learning concepts that will differentiate between healthy controls and people with suspected OPD whose swallows did not exhibit OPD (see Figure 10). Specifically, we will analyze a random 70% training subsample and use the deep belief machine learning approach as in our preliminary work [70]. Once modeling is complete, the remaining 30% validation subsample will be used to obtain accuracy estimates devoid of model overfitting.

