**Table 2 –** Frequency of signal maxima co-occurring with swallow kinematic events; separated by PAS ranges PAS 1-2 vs. PAS 3-8. NUME denotes the number of signal maxima co-occurred with swallow kinematic events > 50% of the time. MIC denotes a microphone, while S-I, A-P, and M-L denote vibrations in superior-inferior, anterior-posterior, and medial-lateral directions captured by an accelerometer.

Sensor	NUME	PAS 1-2		PAS 3-8	
		overall %	range	overall %	range
MIC	80/91	49	37-65	13.6	10-18
S-I	64/91	45	29-62	11	7-16
A-P	55/91	43	26-62	11	6-17
M-L	48/91	40	25-61	10	3-16

**A2.d. Experimental approach:** STEP 1: All swallows from patients and healthy participants (Aim 1) will be rated using the MBSImP. Judges will undergo standardized training in visual inspection and MBSimP ratings of swallow kinematic functions and impairments, and establishment of inter- and intra-rater reliability before beginning scoring. STEP 2: In addition to MBSimP component 16 (pharyngeal residue), pharyngeal residue (valleculae, pyriform sinuses) will be measured using the Normalized Residue Rating Scale which standardizes areas of barium residue retained in pharyngeal recesses (valleculae, pyriform sinuses) using conversion factors based on individual patient height [112]. STEP 3: We will measure airway compromise using the PAS [109]. STEP 4: Pre-process HRCA recordings per steps taken in previous publications [29, 30, 71] to remove any disturbances and diminish noise in these recordings.

STEP 5: We will develop an algorithm based on the state-of-the-art machine learning concepts whose output will be the differentiation between healthy controls and people with suspected dysphagia whose swallows did not exhibit dysphagia, healthy dysphagic (see Figure 11). Specifically, we will utilize a random 70% training subsample for the deep belief machine learning approach as in our preliminary works [70], and once modeling is complete, use the remaining 30% validation subsample to obtain accuracy estimates devoid of model overfitting.

**A2.e. Data interpretation:** We will employ the same deep learning methods as in Aim 1 for our primary analysis, but instead will employ techniques suitable for categorical, ordinal dependent variables such as MBSimP and PAS. In addition, we will employ regression tree and linear mixed model methods in an effort to obtain simpler

**Figure 11 –** Our proposed experimental and data analysis approach for Aim 2.

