means of converting HRCA signals. We will examine performance metrics such as root mean square error and multiple coefficient of determination ( $R^2$ ) to evaluate our score equating models.

**A2.f. Expected outcomes:** The benchmark for success of Aim 2 will be creation of a set of HRCA signal signatures that can be translated to MBSImP, PAS, and pharyngeal retention measures. We anticipate a model can be built with sufficiently high predictive ability so that  $R^2$  and/or root mean square error of score translation is no greater than 5% of the range of the swallowing impairment measure. The major outcome of this aim is that HRCA signal signatures will reflect swallow kinematic and airway protection function and equate to standard measures of swallow impairment which will help us develop the HRCA based Aspirometer as a tool that characterizes and predicts risk of adverse outcomes associated with dysphagia, without imaging.

**A2.g. Challenges and contingency plans:** As in Aim 1, in the highly unlikely event that our VF judges' ratings drift unacceptably, we will increase surveillance on inter- and intra-rater reliability and pull judges from analysis and retrain them to criterion, retest their reliability before placing them back online.

**A2.h. Sample size justification:** The proposed approach is based on nonlinear modeling for which classical sample size calculation procedures are not suitable [125, 126]. As our augmented dataset is expected to contain more than 4000 (existing recordings)+700 (Aim 1) swallows, we strongly believe that it is a sufficient number of swallows as previous publications using similar nonlinear modeling techniques used data sets with a significantly lower number of samples [127-129]. Nonetheless, accounting for an intra-class correlation of 0.7 and a resulting design effect of 3.8 as in Aim 1, and assuming as many as 20 predictors will be needed in a linear model, we will be able to detect statistical significance of an  $R^2$  as small as 0.03 in the training sample and 0.06 in the validation sample with 80% power at  $\alpha=0.05$ .

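### The refitted DeLong comparison of SIS plus HRCA against SIS in A3.e is mis-calibrated; the plan should state one locked HRCA score and one primary comparison

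*Combined protocol and SAP*

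**What the plan says.** A3.e takes presence or absence of clinically significant dysphagia or aspiration as the outcome of logistic models, with "HRCA signatures and SIS, both individually and in combination, as the independent variables. We will use areas under ROC curves (c-statistics". The c-statistics are then compared by DeLong's method, and the expectation is: "We anticipate that the c-statistics for the 3 models involving HRCA will be significantly greater than that using SIS alone". The section does not give the number of HRCA terms or say whether the HRCA input is fixed beforehand. It names no hold-out, cross-validation or optimism correction. No data other than the Aim 3 patients are named for these fits.

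Other sections bear on the point:

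- A1.d STEP 5 does guard against overfitting: "Once modeling is complete, the remaining 30% validation subsample will be used to obtain accuracy estimates devoid of model overfitting". A2.d STEP 5 has the same 70/30 split.
- A2.f sets as the Aim 2 benchmark the "creation of a set of HRCA signal signatures that can be translated to MBSImP, PAS, and pharyngeal retention measures".
- A3.a plans to "compare four levels of screening predictions (SIS human judgment criterion only, HRCA criterion only, SIS and HRCA criteria, SIS or HRCA criteria", and expects 90% sensitivity and specificity "using one of the 3 strategies incorporating HRCA". A3.h words its power claim in the same one-of-three way.
- A3.d STEP 3 says of the concurrent screening: "we will record and denote the output of the algorithm for each observed swallow with findings from Aims 1 & 2".
- A3.h assumes 46 effective patients out of 50, about half with the outcome, a SIS–HRCA correlation of about 0.3, and c = 0.600 for SIS. It claims 80% power for a gain of 0.240 at α = 0.05.

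**The concern.** DeLong's method treats the two scores as given. When both are fitted values from nested models estimated on the same patients, two things go wrong. The larger model can hardly look worse than the smaller one, because its coefficients were chosen to fit those patients. And the standard error ignores that choice. With one added term the null gain is small and rarely reaches significance, so the test is conservative. With several added terms the in-sample gain grows and the test becomes anti-conservative.

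A3.a says that a device that does not outperform SIS does not merit further development, so this comparison has weight. Its error rate depends on what enters the model, and A3.e leaves that open. There is a separate gap: three HRCA strategies may each deliver the win, and no primary comparison or adjustment is given.

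**Working it through.** **Step 1. The plan's own power figure.** Inputs from A3.h: 23 patients with and 23 without the outcome, c = 0.60 against 0.84, correlation 0.3, α = 0.05 (sidedness not stated; taken as two-sided). The Hanley–McNeil variance is [A(1−A) + 22(Q₁−A²) + 22(Q₂−A²)] / 23², with Q₁ = A/(2−A) and Q₂ = 2A²/(1+A).

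- A = 0.60: [0.240 + 22(0.0686) + 22(0.0900)] / 529 = 0.00705, SE 0.0840.
- A = 0.84: [0.1344 + 22(0.0185) + 22(0.0614)] / 529 = 0.00358, SE 0.0598.
- Variance of the difference: 0.00705 + 0.00358 − 2(0.3)(0.0840)(0.0598) = 0.0076, SE 0.0873.
- Power: Φ(0.24/0.0873 − 1.96) = Φ(0.79) ≈ 78.5%.

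This is within two points of the stated 80%, so A3.h is reproduced for one fixed HRCA score.

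**Step 2. Refitted SIS plus HRCA against SIS, with HRCA pure noise.** Monte Carlo, 23 against 23, 5,000 runs per cell. SIS has true c = 0.60, either as pass/fail (60%/60%) or continuous. The k HRCA terms are independent standard normals. A false win is DeLong z > 1.96 in HRCA's favour (nominal 2.5%). The documents do not give k for Aim 3. The value 3 would match the three kinds of measure in A2.f but is not a covariate count; 5 and 10 only show the trend.

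| k | False wins, pass/fail SIS | False wins, continuous SIS | Mean in-sample c (pass/fail SIS) | c in new patients |
|---|---|---|---|---|
| 1 | 1.4% | 0.3% | 0.64 | 0.57 |
| 2 | 4.2% | 1.3% | – | – |
| 3 | 9.9% | 3.1% | 0.69 | 0.56 |
| 5 | 27% | 12% | 0.73 | 0.55 |
| 10 | 77% | 53% | 0.80 | 0.54 |

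Separate repeats agree. At k = 3 with independent terms they gave 8.6–10.7% and 3.3–3.9%. At k = 1 they gave 1.3–2.1% and 0.2–0.5%; the 2.1% came from 800 runs, where the Monte Carlo standard error is √(0.014 × 0.986 / 800) = 0.4 points.

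**Step 3. One HRCA term with real signal.** At a true HRCA AUC of 0.70, nested DeLong has 15–39% power across runs, against 59–71% for the likelihood-ratio test on the same data. At the planned 0.84 nested DeLong has 83–95%, so the loss falls on gains smaller than planned.

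**Step 4. HRCA alone, refitted, truly equal to SIS (both 0.60).** False wins (pass/fail / continuous SIS) are 2.9% / 1.4% at k = 1, 6.4% / 4.1% at k = 3 and 15% / 9% at k = 5. A logistic fit on one predictor leaves its c-statistic unchanged apart from a possible sign flip, so k = 1 shows essentially no inflation.

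**Step 5. Fixed rules, no fitting.** Take HRCA sensitivity = specificity = 60%, as for SIS. If the two are independent within each outcome group, the AND rule has sensitivity 0.6² = 0.36 and specificity 1 − 0.4² = 0.84, so c = (0.36 + 0.84)/2 = 0.60. The OR rule mirrors it. None of the three strategies is truly better than SIS. In simulation (correlation 0 or 0.3) each one wins in 2.6–3.2% of trials and at least one wins in about 5.4–6.3%. At the Bonferroni threshold for three (z > 2.394) the latter falls to 2.4–2.5%.

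**Step 6. One locked HRCA score against SIS, no refitting.** False wins are 2.6–3.5% at equal AUC. Power at 0.84 is about 76–83% with correlation 0.3, and 65–73% if the two are independent.

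**The case against.** The strongest reply is that Aim 3 tests an HRCA output already built, so nothing of substance is refitted. Much supports this:

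- Specific Aims speaks of a deployable tool that is then tested clinically, and of independent HRCA cutoffs from Aim 2.
- Table 1 speaks of deploying a system.
- The timeline (Figure 13) puts algorithm work under Aims 1 and 2 only.
- A3.d STEP 3 records an algorithm output.
- A3.h assumes a single SIS–HRCA correlation.
- The three models in A3.e match the three HRCA strategies in A3.a. SIS, HRCA and their sum would give only two models containing HRCA.
- The plural signatures is generic wording elsewhere in the plan.

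This stands as the more likely intent, and fixed criteria would carry no fitting optimism. It does not close the point. No visible section says that the output is frozen or that it is the A3.e covariate. A3.d records it per swallow, while A3.h counts patients, and neither A3.d nor A3.e gives a rule for combining a patient's swallows. Fixed AND and OR rules need no fitted model, yet A3.e fits models. Figure 12, captioned as the Aim 3 analysis approach, is not visible here and may settle some of this.

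The reply is also right on weight. A3.f counts completed testing as the benchmark, and A3.a sets sensitivity and specificity expectations too, so this comparison is not the sole criterion. Which strategy should be primary is the sponsor's choice, since the A3.a hypothesis covers HRCA both with and without SIS.

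**Conclusion.** The point holds as a calibration and specification problem in a stated method. DeLong between nested refitted models is the wrong test for SIS plus HRCA against SIS. With one HRCA term it is conservative (about 0.2–1.4% false wins against 2.5%) and much weaker than a likelihood-ratio test at AUC 0.70. With three refitted terms it is anti-conservative (about 3–11%), and more so beyond that. If fixed rules are meant, fitting optimism disappears, but the one-of-three route to success still gives about 5.4–6.3% for at least one false win.

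A reader might infer that A3.e as written is bound to favour HRCA falsely, citing the figures for five or ten terms. The documents do not support that: no section gives such a count for Aim 3, and the 20 predictors in A2.h belong to an Aim 2 linear model. Nor do they support the inference that A3.h's 80% power is wrong; it is reproduced for a single fixed score.

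The figures assume 23 against 23 patients, SIS c = 0.60, two-sided α = 0.05, normal HRCA terms and in-sample fitting. The last is inferred from the absence of any other data source in A3.e.

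**What to change.** Bring A3.a, A3.d and A3.e into line, with text in A3.e such as:

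> Before any Aim 3 VF is read, one patient-level HRCA score, its cutoff, and the rule for combining a patient's swallows are fixed from Aims 1 and 2 data. The locked score, or the fixed rules, are compared with SIS by DeLong's method without refitting. Any fitted SIS plus HRCA model is tested by likelihood ratio on the single locked HRCA term, and its c-statistic is reported with optimism correction.

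Then either name one primary comparison or adjust for three. If several signatures are intended, state how many and combine them into one score using Aims 1 and 2 data only. The likelihood-ratio test is near its nominal 5% only with one term: it rejects noise in 5.3–5.6% of runs at k = 1, 6.5–7.1% at k = 3 and 14–15% at k = 10.

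The cost is wording, with no added patients or visits. Reported c-statistics will be somewhat lower, and HRCA cannot be tuned on Aim 3 data. Power for the locked comparison is about 76–83% at AUC 0.84 if the 0.3 correlation holds. Bonferroni for three would cut a nominal 80% to Φ(1.960 + 0.842 − 2.394) = Φ(0.408) ≈ 66%, so naming one primary comparison is the cheaper option.

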## SPECIFIC AIMS

Hundreds of thousands of people annually suffer from compromised nutrition, hydration, and quality of life due to impaired swallowing (oropharyngeal dysphagia or OPD), and aspiration of swallowed food into the respiratory system. OPD leads to aspiration pneumonia (AP) which increases the risk of death during hospitalization threefold, and adds 53,000 annual hospitalization days and nearly \$550 million to US health care costs annually. Through our research, we seek to pre-emptively prevent OPD diagnoses from evolving into aspiration pneumonia, and mitigate these economic and human costs. Gold-standard videofluoroscopy (VF), used to objectively diagnose OPD, is not an appropriate screening tool due to its invasiveness, size and prohibitive cost, and it cannot be deployed immediately upon suspicion of OPD. Standard institutional screening (SIS) protocols are therefore used to predict OPD. But since they rely solely on subjective, non-instrumented human judgment of OPD risk by simply watching the patient swallowing and observing for choking, a) their sensitivity is compromised because half of aspirators do not choke due to silent aspiration, b) their specificity is compromised because up to 60% of nonaspirators cough during SIS, and c) in settings in which subsequent VF is not available or feasible, SIS provide no diagnostic information to guide intervention because they cannot identify the swallowing impairments leading to aspiration.

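### The SIS-alone c-statistic in A3.e comes from a fitted logistic model and so cannot fall below 0.5; this is negligible at the planned 0.600, but it flatters the comparator if SIS performs at or below chance.

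*Combined protocol and SAP*

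**What the plan says.** A3.a sets up the Aim 3 comparison as four screening rules: "SIS human judgment criterion only, HRCA criterion only, SIS and HRCA criteria, SIS or HRCA criteria". Each has a direction. The Significance section explains that patients who fail SIS go on to intervention, and A3.d has staff score the screen by the institutional algorithm, recording signs of OPD.

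A3.e then specifies the analysis: "We will fit a series of logistic regression models with presence/absence of clinically significant OPD/aspiration as the dichotomous dependent variable", with "HRCA signatures and SIS, both individually and in combination, as the independent variables. We will use areas under ROC curves (c-statistics" as the measure of accuracy, compared by DeLong's method. The stated expectation is that "the c-statistics for the 3 models involving HRCA will be significantly greater than that using SIS alone". A3.e gives no fixed score, no sign restriction and no hold-out sample for Aim 3.

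A3.h plans for an effective 46 patients, about half with clinically significant dysphagia or aspiration, an area of 0.600 for SIS alone, and "a correlation of approximately 0.3 between SIS and HRCA". It claims 80% power for an increase of 0.240.

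On how weak SIS may be, Specific Aims says that "half of aspirators do not choke due to silent aspiration, b) their specificity is compromised because up to 60% of nonaspirators cough during SIS".

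**The concern.** A screening test has a direction before any data are seen. If failing turns out to be more common in patients without OPD, its AUC is below 0.5, and that is the honest result. A logistic model with SIS as its only predictor does not report that. It fits a negative coefficient, ranks the patients who passed as the higher-risk group, and returns the mirror-image value.

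The c-statistic is the only comparison measure named in A3.e, and SIS alone is the comparator in every contrast. A floor of 0.5 under the comparator can therefore shrink the very difference that Aim 3 is meant to detect, and most so where SIS is weakest. The reported figure would also describe a rule that nobody applies, in which passing the screen predicts OPD.

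**Working it through.** **Inputs.** From A3.h: 46 patients, 50% prevalence (so 23 with and 23 without OPD), SIS area 0.600, increase 0.240 (HRCA 0.840), correlation 0.3, alpha 0.05. Assumptions not in the documents: one pass/fail SIS value per patient, the split of sensitivity and specificity that gives 0.600, a graded binormal HRCA score, 0.3 read as a within-class latent correlation, and a two-sided test.

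**Step 1: the plan's own power figure.** The Hanley-McNeil variance is [A(1-A) + 22(Q1-A²) + 22(Q2-A²)] / 23², where Q1 = A/(2-A) and Q2 = 2A²/(1+A).
- A = 0.600: variance 0.00705.
- A = 0.840: variance 0.00358.
- Variance of the difference: 0.00705 + 0.00358 - 2(0.3)√(0.00705 × 0.00358) = 0.00761, so SE = 0.0872.
- Power: Φ(0.240/0.0872 - 1.96) = Φ(0.79) = 78.5%.

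This is close to the stated 80%. A one-sided test with the null variance gives 81.0%.

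**Step 2: the reversal.** For a pass/fail screen, c = (sensitivity + specificity)/2. A constructed screen that is positive in 9 of 20 patients with OPD and 11 of 20 without has c = (0.45 + 0.45)/2 = 0.45. The logistic fit gives a SIS coefficient of -0.40 and a model c-statistic of 0.55 = 1 - 0.45. In general the fitted value is max(c, 1-c).

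**Step 3: how often, and how much.** Exact enumeration over Binomial(23, sensitivity) × Binomial(23, specificity):

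| Sensitivity / specificity | True c | Reversed | Mean reported c |
|---|---|---|---|
| 60% / 60% (planned c) | 0.600 | 6.4% | 0.606 |
| 92% / 66% (Daniels, Table 3) | 0.790 | about 0% | 0.790 |
| 50% / 50% | 0.500 | 44% | 0.559 |
| 50% / 40% (Specific Aims at its limit) | 0.450 | 70.5% | 0.571 |

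The last row takes half of aspirators as missed and uses the upper bound of 60% for non-aspirators who cough, so specificity is 100% - 60% = 40%. Other splits that give c = 0.600 reverse in 2.5% to 6.4% of trials.

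**Step 4: effect on the test.** Simulated DeLong power for HRCA alone against SIS alone, correlation 0.3, with SIS in its fixed direction and then with the fitted sign:

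| SIS c | HRCA c | Fixed direction | Fitted sign |
|---|---|---|---|
| 0.60 | 0.84 | 81% | 80% |
| 0.45 | 0.84 | 99% | 79% |
| 0.45 | 0.75 | 89% | 41% |

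The first row is the A3.h case, and its fixed-direction result again agrees with the stated 80%.

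**The case against.** The strongest reply is that the plan does not assume a SIS worse than chance. A3.h sets 0.600. The value of 0.45 arises only by pairing one loose figure with the upper bound of another. Other statements in the same document, that silent aspiration occurs in up to 40% of aspirators (Significance) and that screens identify about 60% of those without OPD (A3.b), give 60%/60%, which is exactly 0.600. Cough is also not the whole screen: A3.d records other signs, such as wet voice. The published screens in Table 3 essentially never reverse. All of this stands, and it confines the point to the case where SIS proves very weak.

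It is also true that the reversal raises the comparator, so it cannot produce a false claim that HRCA is superior to SIS.

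A reader might infer something stronger: that in a joint SIS and HRCA model a negative SIS coefficient would create a spurious gain for the combination. The documents do not support that. At the A3.h inputs an additive model gives a negative SIS coefficient in roughly 40% of trials. But if both scores are treated as binormal, the best linear weight on SIS is proportional to 0.358 - 0.3 × 1.406 = -0.06, so a sign near a coin toss is expected. The consequence is slight: power for the combination against SIS is 93% with the free sign and 94% with it restricted. Where the sign is negative, the gain over HRCA alone averages about 0.007 and is significant in about 0.2% of those trials. A3.e does not plan a test of the combination against HRCA alone. Moreover, its count of three models involving HRCA matches the HRCA-only, AND and OR rules of A3.a. If those rules are the predictors, there is no separate SIS coefficient to reverse. What remains is an ambiguity between A3.a and A3.e.

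**Conclusion.** The point holds in a limited form. As written, the A3.e procedure cannot report a SIS-alone c-statistic below 0.5, although the Significance section, A3.a and A3.d all treat a failed screen as predicting OPD. At the planned 0.600 this is negligible (6% reversals, bias +0.006, about 1 point of power), and at Table 3 performance such as 92%/66% it is essentially nil. If SIS is at or below chance, the mean reported value is 0.56 to 0.57 against a true 0.45 to 0.50. At a true 0.45, power for HRCA against SIS falls by about 20 points (HRCA 0.84) or 48 points (HRCA 0.75).

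The figures rest on 23 patients per class, a single pass/fail SIS result per patient and a within-class correlation of 0.3. The error is conservative for the superiority claim, so nothing here suggests that the plan is tilted towards HRCA. The change is an inexpensive improvement, not the repair of an invalid analysis.

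**What to change.** In A3.e, compute the SIS-alone AUC directly from the screen result with fail taken as OPD predicted. For a pass/fail result this is (sensitivity + specificity)/2, and it may fall below 0.5. Score the HRCA output in the direction set by Aims 1 and 2, and enter these scores, not fitted probabilities, in DeLong's test.

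For the combinations, reconcile A3.a with A3.e by scoring the pre-set AND and OR rules directly. Restricting the coefficients of an additive model to be non-negative is not a substitute: such a model is still neither rule. Reading a binding restriction as proof that SIS adds nothing would be wrong in about 14% of trials when the two screens are uncorrelated within class and SIS does carry information.

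The cost is a few sentences in A3.e and a small change to the analysis code. No extra patients or data are needed, and the sample size is unchanged. The wording should be settled before the Aim 3 data are examined, so that the direction cannot look like a choice made on the result.
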